8.1 Number of Participant and Participant Selection

Adults aged 18 years or older, who are admitted for in-patient care related to IRID (or other co-morbidities) with detectable HCV will be enrolled from Australian hospitals for TOPIC. 60 participants will be enrolled in total: 30 participants in Cohort A and 30 participants in Cohort B.

8.2 Inclusion criteria

Participants must meet all of the following inclusion criteria to be eligible to participate in this study.

- 1) Have voluntarily signed the informed consent form.
- 2) 18 years of age or older.
- 3) Injected drugs within the last 6 months OR be known to be HCV Ab positive
- 4) Hospitalized with an IRI with an anticipated inpatient stay of > 1 weeks¹
- 5) HCV RNA positive
- 6) Compensated liver disease
- 7) Documented non-cirrhotic at enrolment with a qualifying liver FibroScan ≤ 9.5 kpA or an APRI < 2.0
- 8) If co-infection with HIV is documented, the subject must meet the following criteria:
 - a. ART naïve with CD4 T cell count >500 cells/mm³;
OR
 - b. On a stable ART regimen (containing only permissible ART) for >4 weeks prior to screening visit, with CD4 T cell count ≥ 200 cells/mm³ and a plasma HIV RNA level below the limit of detection. Permissible ARTs include:
 - Raltegravir
 - Dolutegravir
 - Rilprvirine
 - Elvitegravir/cobicistat
 - Tenofovir disproxil fumerate
 - Tenofovir alafenamide

- Emtricitabine
- Lamivudine
- Abacavir

¹ Although people who inject drugs are the focus of this study, patients without a recent history of IDU or IRID who are admitted with an expected duration of stay > 1 week may also be included at discretion of study team. In this case the questions on injecting behaviour will be omitted and additional data collected on nature of co-morbidities present.

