Data on the feasibility and success of HCV treatment commenced whilst patients are in hospital are limited. In a recent paper by Post and colleagues from the Prince of Wales Hospital, Sydney, Australia, 100 inpatients underwent opportunistic HCV assessment with the offer of HCV treatment initiated on or just after discharge ⁴. Of 70 viraemic patients, 46 completed the assessment and commenced treatment (21 with DAA on discharge and 20 treated post discharge) and 80% of these went on to achieve SVR12, suggesting that engagement with HCV services during admission could facilitate subsequent treatment. However, a number of patients either did not complete the assessment or did not start treatment, with factors such as access to FibroScan and waiting time for HCV RNA and genotyping results identified as major barriers. Reducing these through the use of non-invasive fibrosis tests, removal of genotyping requirements and the use of POC RNA tests should facilitate rapid assessment and treatment commencement. In the Post study although the majority were admitted with infectious complications, only 26% were current PWID.

Data on testing and engagement in this group is particularly limited. In a recent retrospective clinical audit of HCV testing patterns in PWID admitted with IRID to a single centre Sydney tertiary hospital (Tan et al, AVHEC), only 30% of this group were appropriately tested for HCV during their period of admission, despite the average length of stay being 12 days. Clearly there is missed opportunity for testing, engaging and treating this high risk group during hospital admissions.

One of the greatest challenges to inpatient initiation lies in the completion of the therapeutic course after discharge. During the period of hospitalisation treatment can be observed and support provided, including engagement with drug and alcohol services and the potential provision of peer support workers. However, following discharge competing priorities may limit treatment completion and loss to follow-up is a real concern, thus it is imperative that as much of the treatment course is completed as possible during admission. This can be facilitated by two strategies

- The provision of point-of-care RNA testing on site. This will reduce the anticipated wait time between venepuncture and RNA result by several days and allow for HCV treatment initiation within the first few days of admission.

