7.2 Secondary Objectives

- To evaluate the proportion of patients achieving confirmed SVR12 (undetectable HCV RNA at time point 12 weeks plus post treatment commencement) in patients hospitalised for IRID and commencing inpatient DAA treatment within public hospital services
 - To evaluate and compare the proportion of patients with undetectable HCV RNA at 12 weeks post-treatment (SVR12) within each cohort
 - To evaluate proportion of patients with HCV below LLOQ at week 4 of therapy and ETR
 - To evaluate DAA treatment completion rates
 - To evaluate adherence during treatment via in hospital medication charts and outpatient weekly self-report
 - To evaluate acceptability and feasibility of DAA commencement whilst an inpatient
 - To evaluate adverse events secondary to drug:drug interactions
 - To evaluate performance of finger prick POC testing compared to plasma HCV RNA at screening
 - To evaluate completion of duration of recommended inpatient stay and therapy for co-morbidities
 - To determine effect of HCV treatment on quality of life
 - To evaluate rate of re-call and re-infection at 6, 9- and 12-months post study enrolment
- In those who inject drugs:
- To evaluate engagement with D&A services and rates of OST initiation
 - To determine rates and patterns of injecting behaviour following therapy for HCV

8 Participant population

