15.2 Secondary Endpoints

- Proportion of patients with HCV RNA below the level of detection at 12 weeks post-treatment (SVR12) within each cohort by both ITT and PP analyses
- Proportion of patients with HCV below LLOQ at week 4 of therapy and ETR
- Proportion of patients completing DAA treatment course
- Proportion of patients with full (100%) and partial adherence (<50%, 50-80%, 81-99%) during treatment as assessed by in hospital medication charts and outpatient weekly self-report
- Uptake of DAA therapy during admission in patients suitable for study
- Safety: Rates and predictors of adverse events secondary to drug:drug interactions
- Sensitivity and specificity of finger prick POC testing compared to plasma HCV RNA at screening
- Proportion of patients completing recommended inpatient stay
- Changes in HRQOL
- Rates of re-attendance at subsequent planned study visits
- Rates and predictors of reinfection during follow-up

In those with a history of injecting drug use:

- Proportion of patients undergoing D&A evaluation during admission
- Proportion of patients initiating OST during admission
- Frequency and patterns of injecting behaviour following therapy for HCV

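### Footnote 1 to the inclusion criteria drops the injecting questions for some participants whom the injecting-behaviour endpoint includes, and it conflicts with section 11

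*Protocol*

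**What the plan says.** Four parts of the protocol bear on who is asked about injecting.

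- **Entry (8.2 and synopsis).** Criterion 3 reads "Injected drugs within the last 6 months OR be known to be HCV Ab positive", so recent injecting is not required. Criterion 4 asks for an injecting-related infection (IRID), but its footnote 1 also allows, at the study team's discretion, "patients without a recent history of IDU or IRID who are admitted with an expected duration of stay > 1 week". It then sets a data rule: "In this case the questions on injecting behaviour will be omitted and additional data collected on nature of co-morbidities present".
- **Endpoints (15.2 and synopsis).** Under the heading "In those with a history of injecting drug use" stands "Frequency and patterns of injecting behaviour following therapy for HCV". Outside that heading, and so for all participants, stands "Rates and predictors of reinfection during follow-up".
- **Objective (7.2 and synopsis).** The matching objective is "To determine rates and patterns of injecting behaviour following therapy for HCV". Its heading is in the present tense and covers people who inject drugs, a narrower group than the endpoint's.
- **Data collection (section 11; schedules in sections 3 and 4).** The behavioural questionnaire is due at Screening, SVR12 and SVR48. Its content includes injecting risk behaviours. Neither section 11 nor the schedules mention the footnote's exception.

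**The concern.** The footnote decides who is asked by status at entry, whereas the endpoint decides who counts by lifetime history. A person who injected in the past, is antibody positive and is admitted for an unrelated illness falls between the two: in the endpoint population, but not asked.

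The endpoint concerns behaviour after treatment. In such a person the event of interest is a return to injecting, and the rule prevents it from being recorded. If that person is reinfected, the virology will show it, but the post-treatment exposure most directly linked to it will be absent. Data not collected at SVR12 and SVR48 cannot be restored by a statistical analysis plan. Sites also have two instructions that cannot both be followed: the footnote's omission and section 11's questionnaire for participants generally.

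**Working it through.** The protocol states no figure on this point, so there is none to reproduce. The check is a comparison of texts, followed by a simple range.

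**Step 1. Who is asked and who counts, if the footnote is followed.** The footnote's phrase can mean lacking both recent injecting and an IRID (the natural reading) or lacking either one.

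| Participant | Route of entry | In the 15.2 injecting population? | Asked about injecting? |
|---|---|---|---|
| Recent injector with IRID | Criteria 3 and 4 | Yes | Yes |
| Former injector with IRID | Criteria 3 (antibody) and 4 | Yes | Yes, on the natural reading |
| Former injector, no IRID | Footnote 1 | Yes | **No** |
| Current injector, no IRID | Footnote 1, only if read as lacking either | Yes | **No**, on that reading |
| Never injected, no IRID | Footnote 1 | No | No, and nothing is lost |

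The third row is a gap on both readings and the fourth on one. The footnote does not define recent; the only time limit nearby is the 6 months in criterion 3.

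**Step 2. Whether another source fills the gap.** From the schedules:

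- Medical history is taken at Screening and hospital discharge only.
- The drug and alcohol evaluation is at Baseline and Week 4 only (Week 4 is end of treatment in Cohort B).
- Concomitant medication during follow-up is limited to drugs that interact with HCV treatment.
- The questionnaire's drug and alcohol items are listed separately from its injecting items.

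No other scheduled instrument is stated to record injecting at SVR12 or SVR48.

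**Step 3. How many could be affected.** Planned enrolment is 60 (8.1). Let s be the share entering by the footnote, which the protocol neither states nor caps, and f the fraction of those who have ever injected, also not stated. Then affected = 60 × s × f. Assumed values of s give the number of footnote entrants:

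- s = 10%: 0.10 × 60 = 6
- s = 25%: 0.25 × 60 = 15
- s = 50%: 0.50 × 60 = 30

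These are ceilings for the number affected on the natural reading, because f is at most 1.

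**Step 4. Why the population wording matters (all rates assumed).** Take 40 recent injectors, 60% injecting at SVR12, and 20 former injectors who entered by the footnote, 10% injecting.

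- Recent injectors only: 0.60 × 40 = 24, and 24/40 = 60%.
- Anyone with a history of injecting: (24 + 0.10 × 20)/60 = 26/60 = 43%.

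Each figure answers a legitimate question. The first is closer to the objective in 7.2, the second to the endpoint in 15.2. Under the footnote only the first can be computed, and the 2 people who resumed are not seen.

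**The case against.** The strongest reply is that footnote and objective fit each other: the trial focuses on people who inject, the objective says so, and the heading in 15.2 is merely loose. Tightening that heading would remove the mismatch without asking anyone more questions. This stands as an alternative repair. It does not show that the present text is consistent, and it would give up any view of relapse to injecting among former injectors.

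Section 11, read alone, gives the questionnaire to everyone, so the data may be collected after all. That is true if sites follow section 11 rather than the footnote, but the protocol does not say which prevails.

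The predictors of reinfection are not listed, and choosing them is ordinary analysis-plan work. Recency of injecting at entry must be known in order to apply the footnote, so it could still serve as a predictor. Both points stand; what is lost is injecting behaviour after treatment, in the footnote subset.

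A reader might infer more than the text supports in three ways:

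- **That former injectors as a group have no data.** On the natural reading, those admitted with an IRID keep the questions. Even footnote entrants still have the drug and alcohol evaluation, the general drug-use items, HCV RNA, and sequencing if viraemia recurs.
- **That about 44 of 60 would lack injecting data.** This takes the inpatient study in section 5, where "although the majority were admitted with infectious complications, only 26% were current PWID", and computes 0.74 × 60 = 44.4. That study enrolled inpatients opportunistically and is cited as a contrast to this trial's target group. The sum also counts patients with an IRID who would be asked and people who never injected.
- **That reinfection rates are biased.** RNA testing at every follow-up visit does not depend on the survey.

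**Conclusion.** The point holds in a limited form. Footnote 1, section 11, the objective in 7.2 and the endpoint in 15.2 do not agree on who is to be asked about injecting. If the footnote is followed, footnote entrants with past injecting are in the endpoint population without injecting-behaviour data, and no analysis can recover it. If the footnote is read as lacking either condition, current injectors without an IRID are lost as well.

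The size cannot be fixed from the document. The 6 to 30 footnote entrants rest on the assumed 10-50% share, and only those who have ever injected matter. The affected endpoints are secondary, in a study with no formal sample size; primary SVR12 and the reinfection rate are untouched. The change is worth making because it is cheap beforehand and impossible once the visits have passed.

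**What to change.** 1. Delete the omission of the injecting questions from footnote 1 in both the synopsis and 8.2. The additional co-morbidity data can stay.
2. At Screening, ask every participant whether they have ever injected and when they last did. Those who never injected skip the remaining injecting items.
3. At SVR12 and SVR48, ask the injecting items of anyone with lifetime injecting.
4. Use one population wording (any history of injecting) in 7.2, 15.2, the synopsis and section 11, and report results by recent versus past injecting at entry, with recent defined.

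If the sponsor prefers to keep the omission, the minimum is to restrict the endpoint to those who are asked, state the exception in section 11 and the schedules, and say how participants not asked are handled in the reinfection predictor analysis.

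The cost is a wording amendment and a changed skip pattern in a survey already scheduled for all participants at these three visits. The downside is a few more minutes of questions for former injectors.

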8.3 Exclusion criteria

Participants who meet any of the following exclusion criteria are not to be enrolled in this study.

- 1) Inability or unwillingness to provide informed consent or abide by the requirements of the study
- 2) Actively intoxicated.

Participants who meet any of the additional exclusion criteria are not to be treated in this study.

- 3) History of any of the following:
 - a) Clinical hepatic decompensation (i.e. ascites, encephalopathy or variceal haemorrhage)
 - b) Solid organ transplant
 - c) History of severe, life-threatening or other significant sensitivity to study drugs (glecaprevir/pibrentasvir/sofosbuvir) or any excipients of the study drugs
- 4) Creatinine clearance (CLcr) < 30 mL/min at screening (Cohort B only)
- 5) Pregnant or nursing female
- 6) Decompensated liver disease
- 7) Use of prohibited concomitant medications
- 8) Chronic use of systemically administered immunosuppressive agents (e.g. prednisone equivalent > 10 mg/day for >2 weeks)
- 9) Prior treatment failure with an NS5A based DAA regimen

9 Study design

9.1 Summary of study design

[figure not shown]
The study will be conducted as a Phase IV open-label single-arm multicenter study consisting of two sequential cohorts: Cohort A (8 weeks of glecaprevir/pibrentasvir) and Cohort B (4 weeks of sofosbuvir/glecaprevir/pibrentasvir).

9.2 Visit Schedule

Participants will be invited for Screening whilst they are inpatients of the hospital. Participants will be screened for a detectable HCV RNA using standard HCV RNA assays per their local laboratory and the Xpert® HCV Viral Load assay.

Eligible participants will be treated through standard of care with the applicable treatment regimen as per their enrolled cohort. All participants will commence treatment whilst they are inpatients and subsequent visits whilst on-treatment will be completed during their hospital stay where possible. For participants who are discharged before treatment completion, a hospital discharge visit will be conducted. These participants will continue their on-treatment visits through outpatient viral hepatitis services and receive weekly contact to measure treatment adherence.

Following the end of treatment, participants will be reviewed at 12, 24, 36 and 48-weeks post-treatment (SVR12, SVR24, SVR36 and SVR48). At follow-up visits, HCV RNA will be measured using the Xpert® HCV Viral Load assay. If HCV RNA is detected at a follow-up visit, local laboratory HCV RNA and genotype will be measured to determine re-infection.

9.3 Treatment discontinuation

Participants who cease study medication will, wherever possible, continue to be followed up according to the protocol study plan by completing the End of Treatment visit at the time of treatment termination and follow-up visits as per protocol. Participants may revoke consent for follow-up without jeopardizing their relationship with either their doctor or the UNSW/Sponsor. If a participant revokes consent then, if possible, all assessments scheduled for the final visit should be completed.

9.4 Unplanned discharge from hospital

In the event a participant is discharged unexpectedly from hospital prior to treatment completion (either self discharge against medical advice (DAMA) or discharge by medical staff e.g. over a weekend), then the study nurse should attempt to make contact with the patient as soon as is possible. Patient should be encouraged to remain on study drug and access to supply facilitated. Study nurse should complete an Early Discharge CRF and the participant should remain in the study as per study assessment schedule.

10 Treatment of participants

10.1 Treatment

Details of the study drugs are presented in Table 1.

Table 1 Summary of study drugs

	Cohort A	Cohort B
Study Drug	Glecaprevir/Pibrentasvir (Mavyret)	Sofosbuvir/Glecaprevir/Pibrentasvir
Dosage Form	3 x co-formulated tablets of glecaprevir (100mg) and pibrentasvir (40mg)	1 x sofosbuvir (400mg) and 3 x co-formulated tablets of glecaprevir (100mg) and pibrentasvir (40mg)
Mode of Administration	Oral	Oral
Dose Strength	Glecaprevir 300mg Pibrentasvir 120mg	Sofosbuvir 400 mg Glecaprevir 300mg Pibrentasvir 120mg
Duration of Treatment	8 weeks	4 weeks

10.2 Dosing and Administration

Participants should be instructed to take study medication with food at approximately the same time each day. Dose modifications are prohibited. The first study drug dosing will commence in hospital at Baseline (day 0). The start date and the last dose of the regimen should be documented in the subject's source documents and appropriate eCRF.

Participants should be instructed to swallow the study drug tablets whole. Participants should be instructed to only remove the tablets from the packaging immediately prior to dosing.

For a missed dose of study drug, participants should be instructed to take the missed dose of study drug as soon as possible during the same day. However, no more than the daily dose of sofosbuvir and glecaprevir/pibrentasvir should be taken on any calendar day. Participants should be cautioned never to double the next dose with a missed dose of study drug under any circumstances.

Dispensing

Participants will be dispensed with their study medication daily prior to hospital discharge. At the hospital discharge visit, participants will be dispensed with the remaining study medication for the treatment regimen. Participants should receive counseling on the importance of adherence in regard to virologic response and potential development of resistance.

Adherence

Adherence monitoring will be daily observed, and the date and time will be recorded in the medical records prior to hospital discharge. Following hospital discharge, participants will be contacted weekly for self-reported treatment adherence.

10.3 Prior and concomitant medications

The prescribing information for all concomitant drugs should be consulted and reviewed carefully. The determinations listed in the respective contraindicated, warning, and precaution sections must be respected in order to prevent any potentially serious and/or life-threatening drug interactions.

Drug-drug interactions for each participant should be assessed on <http://www.hep-druginteractions.org/>. In case of any questions on potential interactions with a drug, please contact the study principal investigator.

Use of medications listed below within 2 weeks or 10 half-lives, whichever is longer, prior to study drug administration is contra-indicated (see Tables 1 and 2):

Table 2 Contraindicated concomitant medications with glecaprevir/pibrentasvir

Drug Class	Drug(s) within Class that are Contraindicated	Clinical Comments
Anticoagulants	Dabigatran	May increase dabigatran concentration potentially increasing risk of bleeding
Anticonvulsants	Carbamazepine	May decrease DAA exposure leading to a potential loss of therapeutic activity.
Antimycobacterial	Rifampin	May decrease DAA exposure leading to a potential loss of therapeutic activity.
Ethinyl estradiol-containing products	Ethinyl estradiol-containing medications (such as combined oral contraceptives and hormone replacement therapy)	Potential for ALT elevation
Gastrointestinal pro-kinetic agent	Cisapride	
Herbal Product	St. John's Wort (Hypericum perforatum)	May decrease DAA exposure leading to a potential loss of therapeutic activity.
HIV non-nucleoside reverse transcriptase inhibitor	Efavirenz Etravirine Nevirapine	May decrease DAA exposure leading to a potential loss of therapeutic activity.
HIV protease inhibitor	Atazanavir Darunavir	Potential for ALT elevation
HMG-CoA Reductase Inhibitors *	Atorvastatin Lovastatin Simvastatin	Potential for myopathy including rhabdomyolysis.

Immunosuppressant	Cyclosporin	Co-administration not recommended with cyclosporin dose >100mg per day
-------------------	-------------	--

* Some HMG-CoA reductase inhibitors (including atorvastatin, lovastatin, or simvastatin) should not be taken with glecaprevir/pibrentasvir. Participants receiving these statins should either switch to pravastatin or rosuvastatin prior to the first dose of study drug or interrupt statin therapy throughout the treatment period and until 30 days after the last dose. If switching to or continuing pravastatin or rosuvastatin, it is recommended to reduce the pravastatin dose by 50% or limit the rosuvastatin dose to 10 mg daily while on treatment.

Table 3 Contraindicated concomitant medications with sofosbuvir

Drug Class	Drug(s) within Class that are contraindicated	Clinical Comments
Analeptics	Modafinil	Coadministration of sofosbuvir with modafinil is expected to decrease the concentration of sofosbuvir, leading to reduced therapeutic effect of sofosbuvir. Such coadministration is not recommended.
Antiarrhythmics	Amiodarone	Coadministration of amiodarone with another direct acting antiviral may result in symptomatic bradycardia. If coadministration is required, cardiac monitoring is recommended.
Anticoagulants	Vitamin K agonists	Close monitoring of the INR is recommended, as liver function may change with sofosbuvir treatment.
Anticonvulsants	Carbamazepine Phenytoin Phenobarbital Oxcarbazepine	May decrease DAA exposure leading to a potential loss of therapeutic activity, therefore not recommended.
Antimycobacterials	Rifabutin Rifampin Rifapetine	May decrease DAA exposure leading to a potential loss of therapeutic activity, therefore not recommended.
Herbal Supplements	St John's wort	May decrease DAA exposure leading to a potential loss of therapeutic activity, therefore not recommended.
HIV Protease Inhibitors	Tipranavir Ritonavir	May decrease DAA exposure leading to a potential loss of therapeutic activity, therefore not recommended.

11 Study procedures

Screening Visit (Week -6 to Week 0) – All participants

- Informed consent: At the screening visit, participants will provide written and informed consent prior to any study-specific procedures.
- Medical history: A medical history will be taken
- Physical measurements: Height and body weight.
- Clinical laboratory tests: At a minimum, liver function tests, biochemistry and full blood count tests will be collected at Screening (or used from admission bloods).
- HCV RNA (local laboratory): Quantitative HCV RNA
- HCV Genotype (local laboratory): HCV genotype should be collected at screening. Historical participant genotype results are acceptable if these were conducted within 5 years from Screening.
- HCV RNA (point-of-care): A finger-stick capillary whole-blood sample will be collected for the GeneXpert. This may be repeated if an invalid result is obtained in the absence of a local laboratory HCV RNA.

- HIV and HBV serology: Anti-HIV Ab and HBsAg results within 5 years prior to Screening are also acceptable.
- Fibrosis Assessment: Liver fibrosis will be measured using a FibroScan where possible. An AST to Platelet Ratio Index (APRI) will be considered as an acceptable alternative if a FibroScan is not possible.
- Pregnancy test: All females of child-bearing potential will have a serum or urine pregnancy test. This will not be required for females of non-childbearing potential. Determination of postmenopausal status will be recorded during the Screening period based on participant history.
- Behavioural survey and EQ-5D-5L.
- Clinical assessment and concomitant medication assessment / DDI assessment.
- Dried Blood Spot sample.

The following study visits are for participants who commence treatment only.

Baseline visit (Week 0)

Eligible participants who meet the treatment inclusion criteria and meet none of the exclusion criteria will proceed to the baseline visit. This visit must be completed prior to hospital discharge.

The following procedures will be conducted:

- Concomitant medications / DDI assessment: These will be updated from the Screening visit as necessary.
- Pregnancy test: Urine or serum pregnancy tests.
- Full blood count and biochemistry
- Treatment initiation: Participants will be administered the study drug at the site with dosing instructions at the baseline visit.

Week 4 (Cohort A only)

Participants in Cohort A will have an on-treatment visit at Week 4. The following procedures will be conducted:

- HCV RNA testing (local laboratory)
- Pregnancy test (women of child-bearing potential; serum or urine)
- Concomitant medication assessment / DDI assessment
- Adherence

End of Treatment – (Week 8 – Cohort A, Week 4 – Cohort B)

The date of the last dose of study medication will be collected. The end of treatment visit will be either Week 8 or Week 4, depending on the cohort. The following procedures will be conducted:

- HCV RNA testing (local laboratory)
- Liver function tests
- Pregnancy test (women of child-bearing potential; serum or urine)
- Concomitant medication assessment / DDI assessment
- Adherence

Follow-up Visits (SVR12, SVR24, SVR36 and SVR48)

Participants will return for follow-up visits every 12 weeks after the last dose of study medication.

All participants will have the following procedures conducted:

- HCV RNA testing (local laboratory or point of care)
- Behavioural survey and EQ-5D-5L: Participants will complete this questionnaire at SVR12 and SVR48.
- Liver function tests
- Concomitant medication assessment / DDI assessment (SVR12 only)

If a participant is found to be HCV RNA positive at SVR12, additional procedures will be conducted to determine re-infection/relapse. These procedures are:

- HCV Genotype
- Dried Blood Spot Sample for sequencing
- EDTA Plasma for resistance testing (10mL)

All on-treatment visits will be conducted whilst the participant is still an in-patient. If the participant is discharged prior to treatment completion, visits will be conducted through outpatient viral hepatitis services.

Questionnaires

Health Outcomes Survey (EQ-5D-5L)

The EQ-5D-5L provides a simple descriptive profile and a single index value for health status. This information can then be translated into a health utility, which can be used for cost-effectiveness analyses.

Behavioural Questionnaire

Participants will complete a behavioural questionnaire at Screening, SVR12 and SVR48. The behavioural questionnaire will collect information on demographics, drug and alcohol usage, injecting risk behaviours.

12 Recording and reporting Adverse Events (AEs)

